17.7. SUBGROUP ANALYSIS OF SAFETY VARIABLES

Adverse events will be presented by the subgroups of region, race, gender, and age (See [Section 17.1.5](#)).

18. PHARMACOKINETIC ANALYSIS

All PK analysis will be performed using PK population.

Blood sample for plasma concentrations of R-amisulpride, S-amisulpride, total amisulpride, and/or plasma prolactin measurement will be collected at Visit 1/Screening (only for plasma prolactin), Visit 2/Baseline/Day -1, Visit 4/Week 2, Visit 6/Week 6, and Visit 7/Follow-up/Week 7. The PK collection times from Predose on Day -1 to Follow-up and deviations and/or any values excluded from analysis will be presented in data listings. Any plasma concentration or summary statistics below the lower limit of Document:

Author:

Version Number:
Version Date:

V2.0

21MAY2020

Template No: CS_TP_BS016 Revision 4
Effective Date: 01Apr2016

Reference: CS_WI_BS005

quantification (LLOQ) will be represented by "BLQ" (below the limit of quantification) in tables and listings. Amisulpride plasma concentration will not be presented for the placebo group.

R-amisulpride, S-amisulpride, total amisulpride, and plasma prolactin concentrations at each scheduled sample collection time point (including ET and Follow-up, see [Section 6.3](#) for mapping of the ET visit) will be summarized descriptively (n, mean, median, minimum, maximum, coefficient of variation [CV] and if appropriate, geometric mean and geometric CV [GCV]). In addition, if there is at least 1 concentration < LLOQ within a treatment group at a time point, it will be set to $\frac{1}{2}$ LLOQ for summary statistics calculations. A second approach will be to assume a truncated normal distribution for the specific concentration data if at least 10% of the concentrations at a time point are < LLOQ within a treatment group. The mean and variance of truncated normal will be calculated ([APPENDIX 3](#)). Number and percentage of concentrations that are below the LLOQ will be provided for each visit. All PK summaries will be presented by dose.

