^c Visit 6 is the End of Treatment/Early Termination visit. Subjects who discontinue the study prior to Visit 6 will have all Visit 6 procedures performed at the time of discontinuation. All subjects who complete the treatment period and those who discontinue early will complete a follow-up visit 7 (±2) days after the last dose of study drug.

^d Clinical site staff will record the date and time of the 3 doses prior to the study visit in the source (all visits) and CRF (Visits 4 and 6 only), based on subject self-report.

Footnotes continue on next page.

^e Instruct subject to record dosing date and time of the last 3 doses prior to the study visit on the blisterpack wallet and bring back all used/unused study drug and packaging to next visit.

^f Includes a psychiatric history form that will include variables related to duration of illness, treatment response (eg, prior medications used to treat bipolar disorder) and other similar variables.

^g The SCID-5-CT will be used to support the DSM-5 diagnosis and must be administered by a qualified rater at the site.

^h BMI will be calculated by clinical site staff at Screening and recorded in the CRF. At visits 2, 6, and 7, BMI does not need to be calculated by the clinical site staff as it will be calculated in the analysis.

ⁱ Vital signs measurements will include orthostatic changes in blood pressure and heart rate. After being in a supine position for \geq 5 minutes, systolic and diastolic blood pressures, respiratory rate, pulse rate, and temperature will be collected. Blood pressure and pulse rate will be taken again after standing for 2 to 4 minutes. The same arm should be used during each assessment of blood pressure and pulse rate throughout the study.

^j To be eligible for enrollment, subjects must have a MADRS total score \geq 22 at Screening. Subjects who demonstrate a decrease (improvement) of \geq 25% in MADRS total score from Screening to Baseline, or who have a MADRS total score $<$ 22 at Baseline will not be eligible for enrollment (see [Section 24, Appendix V](#)).

^k To be eligible for enrollment, subjects must have a YMRS total score \leq 12 at Screening.

^l At the Screening visit, the baseline/screening version will be completed; for all subsequent visits, the “Since Last Visit” version of the C-SSRS will be administered.

^m Any positive urine β -human chorionic gonadotropin (hCG) test should be confirmed by serum β -hCG.

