13. TERMINATION OF SUBJECT FROM STUDY/ DISCONTINUATION OF STUDY DRUG

13.1. Criteria for Subject Termination

Subjects may terminate the study participation at any time for any reason.

The possible reasons for the termination of study participation are as follows:

- Adverse event.
- Lack of efficacy (specify).
- Lost to follow-up (specify).
- Pregnancy.
- Withdrawal by subject (specify).
- Non-compliance with study drug (specify).
- Protocol deviation (specify).
- Death
- Other (specify).

If at any time during the course of the study, in the opinion of the Investigator, the subject may no longer safely participate due to a change in medical status (eg, experiences an AE, becomes pregnant), the subject must be discontinued from the study drug.

Subjects who, at any study visit post-baseline have a QTcF value greater than 500 ms, who have a > 60 ms increase in QTcF from baseline, or who experience a life-threatening arrhythmia will be discontinued from the study drug and followed until the event resolves; in addition, an adverse event will be reported.

Subjects who develop adverse events of amenorrhea, gynecomastia, or galactorrhea are to be discontinued from the study drug. The reason for discontinuation and information on the epoch will be recorded on the appropriate CRF. In case of death, the date of death should be captured on the CRF.

Subjects who prematurely terminate the study participation will not be replaced.

Subjects who discontinue prior to Visit 6 (Day 42 [± 2]) will undergo procedures and assessments scheduled for Visit 6 (Day 42 [± 2]) at the time of early discontinuation (see [Section 11.6.3](#)).

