2	-1	Predose
4	14 (\pm 2)	Postdose*
6	42 (\pm 2)	Postdose*
7	49 (\pm 2)	Follow-up**

* Sample will be collected after dosing is given on that day. Actual date and time will be recorded.

** Actual date and time will be recorded.

COLLECTION REQUIREMENTS:

Collect 4 mL blood sample into a K₂EDTA (ethylenediaminetetraacetic acid) treated Vacutainer® (or equivalent) tube at each time point. Invert gently 8 to 10 times to mix well. Keep the blood collection tube on wet ice prior to centrifugation, and centrifuge for 10 minutes at x 1500 g to isolate plasma within 30 minutes of blood collection. To ensure a more homogenous sample, all plasma samples should first be transferred to 1 tube and mixed well (by repeatedly aspirating and dispensing the sample into the storage tube). Split the sample with approximately equal volume into 2 polypropylene tubes, and label as Set-1 and Set-2. Store plasma tubes at approximately -70°C freezer within 1 hour until shipping to the bioanalytical lab. The date and time of blood collection must be recorded.

All samples will be shipped with dry ice protection. Set-1 samples will be shipped to the Bioanalytical Lab for R- and S-amisulpride concentration measurements, and Set-2 samples will be shipped to another lab for prolactin concentration measurement.

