6.3. DERIVED TIME POINTS

As per protocol, Visit 6 can be an End of Treatment (EOT) visit or an Early Termination (ET) visit. If a subject terminates early, his/her ET visit will be mapped to the next planned assessment visit if it is within the window of the next planned assessment visit. This applies to both efficacy and safety data. If assessments from an ET visit cannot be mapped to the next planned assessment visit, these assessments will be excluded from any mixed model for repeated measures (MMRM) or analysis of covariance (ANCOVA) analysis. No follow-up visit data will be included in any MMRM/ANCOVA analyses. In the case of the ET being out of window of the next planned visit, it will be mapped to an unscheduled visit as appropriate.

All applicable by-visit efficacy and safety tables will include descriptive statistics for the Follow-up visit and the "Last observation visit". The "Last observation visit" is defined as the post-baseline visit at which the last non-missing observation is collected for a subject for a given parameter, including unscheduled visits or unmapped ET visits. The "Last observation visit" will be excluded from any MMRM/ANCOVA analyses.

For remapping of the ET visits, see Table 1 below.

Table 1: Mapping of the ET visit.

Parameter	Early Termination Day Criteria	Week	Analysis Visit
ECG, Vital Sign, YMRS, C-SSRS, Concomitant Medication, Last dose of Benzodiazepines/ Sedatives/Hypnotics	1 ≤ study day ≤ 9	1	Visit 3/Week 1
	10 ≤ study day ≤ 16	2	Visit 4/ Week 2
	17 ≤ study day ≤ 30	4	Visit 5/Week 4
	31 ≤ study day ≤ 44	6	Visit 6/Week 6
MADRS, CGI-BP-S, HAM-A, QIDS-SR16, AIMS, BARS, SAS	1 ≤ study day ≤ 9	1	Visit 3/Week 1
	10 ≤ study day ≤ 16	2	Visit 4/Week 2
	17 ≤ study day ≤ 30	4	Visit 5/Week 4
	31 ≤ study day ≤ 44	6	Visit 6/Week 6
SDS, EQ-5D-5L, Weight, BMI, Waist Circumference, PWC, HbA1C, Lipid panel, Serum Insulin, HOMA-IR, CRP	1 ≤ study day ≤ 44	6	Visit 6/Week 6

Document:

Author:

Version Number:

V2.0

Version Date:

21MAY2020

Template No: CS_TP_BS016 Revision 4
 Effective Date: 01Apr2016

Reference: CS_WI_BS005

Hematology, Serum Chemistry*, Urinalysis, Serum Prolactin, PK, Plasma Prolactin	1 ≤ study day ≤ 16	2	Visit 4/Week 2
	17 ≤ study day ≤ 44	6	Visit 6/Week 6

* Except for parameters listed above such as HbA1C, Lipid panel, Serum Insulin, HOMA-IR, CRP.

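### Early-termination PK and prolactin samples are assigned to Week 2 or Week 6 by study day alone, so any drawn after drug was stopped would be pooled with postdose samples

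*SAP*

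**What the plan says.** **Mapping rule.** SAP 6.3 sets the rule for anyone who leaves before the planned end of treatment: "his/her ET visit will be mapped to the next planned assessment visit if it is within the window of the next planned assessment visit". Table 1 gives the windows. The row for "Hematology, Serum Chemistry*, Urinalysis, Serum Prolactin, PK, Plasma Prolactin" has two: "1 ≤ study day ≤ 16" goes to Week 2 and "17 ≤ study day ≤ 44" goes to Week 6. SAP 6.1 counts study day from the first dose.

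**Use of mapped values.** SAP 18 summarises R-, S- and total amisulpride and plasma prolactin "at each scheduled sample collection time point (including ET and Follow-up", refers back to SAP 6.3 for the ET mapping, and presents the PK summaries by dose. Concentrations below the limit of quantification (0.0500 ng/mL) are set to half of it. SAP 17.2 tests the Week 6 change in serum prolactin against placebo by rank ANCOVA, overall and by sex, in the safety population. SAP 6.3 keeps ET values out of ANCOVA only when they cannot be mapped.

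**What the samples are meant to be.** Protocol Appendix III labels the Visit 4 and Visit 6 samples postdose: "Sample will be collected after dosing is given on that day".

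**When the ET visit happens.** Protocol Table 2, footnote c: "Subjects who discontinue the study prior to Visit 6 will have all Visit 6 procedures performed at the time of discontinuation". No maximum interval from the last dose is given.

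**The concern.** The Week 2 and Week 6 labels carry a meaning, namely a level measured on drug on the day of a dose. The mapping rule looks only at time since the first dose, so it cannot tell an ET sample taken hours after a dose from one taken a week after the last dose.

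Off-drug ET samples are foreseeable. Protocol 13.1 requires study drug to be stopped for several events, for example: "Subjects who develop adverse events of amenorrhea, gynecomastia, or galactorrhea are to be discontinued from the study drug". Protocol 17.3 separates stopping medication from leaving the study, so a gap between last dose and ET visit can arise.

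Two outputs are exposed. The first PK objective is the therapeutic plasma concentration range at 200 and 400 mg/day, and the by-dose tables describe those concentrations. The Week 6 serum prolactin test is a comparative safety analysis, and subjects stopped for prolactin-type events may contribute to it a value drawn after drug was stopped.

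**Working it through.** The plan states no figure on this point, so there is none to reproduce. The check has three parts.

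**1. Apply the Table 1 windows.** ET on Days 1, 3, 14 or 16 maps to Week 2. ET on Days 17, 20, 24 or 44 maps to Week 6. Day 45 is unmapped. A subject who takes the last dose on Day 17 and attends ET on Day 24 has been off drug for 24 - 17 = 7 days and is summarised as Week 6. The planned follow-up sample is also taken 7 (± 2) days after the last dose, yet SAP 6.3 Table 2 keeps it as its own time point. The plan thus separates off-drug samples in one place and pools them in the other.

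**2. Look for a rule that removes them.**
- SAP 5.4 requires at least one valid postdose concentration without deviations or events that could affect PK. That admits subjects. A subject with a valid Week 2 sample qualifies, and the text does not say which of that subject's later samples are dropped.
- SAP 10.1 says that events affecting PK quality may be treated as significant and the data left out of the summaries. Its nearest example is inaccurate dosing on the sampling day. It does not name stopped drug, and it treats deviations in blood collection time as not significant.
- Serum prolactin is safety laboratory data, which SAP 10.1 does not cover.

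**3. Size.** Let p be the share of a visit's samples that are off drug and r their level as a fraction of the on-drug level. Both are assumptions. Then:
- geometric-mean ratio = r^p
- arithmetic-mean ratio = 1 - p(1 - r)

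| p | r | Geometric | Arithmetic |
|---|---|---|---|
| 2% | 0.5 | 0.986 | 0.990 |
| 5% | 0.1 | 0.891 | 0.955 |
| 5% | 0.01 | 0.794 | 0.951 |
| 5% | 0.001 | 0.708 | 0.950 |
| 10% | 0.1 | 0.794 | 0.910 |
| 10% | 0.01 | 0.631 | 0.901 |
| 10% | 0.001 | 0.501 | 0.900 |
| any | 1 | 1 | 1 |

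For scale, 5% of 98 randomised subjects per arm is about 5 subjects (0.05 × 98 = 4.9).

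If the off-drug values are below quantification and set to 0.025 ng/mL, and the on-drug level is assumed to be 10 to 500 ng/mL, p = 5% gives a geometric ratio of (0.025/10)^0.05 = 0.741 to (0.025/500)^0.05 = 0.609. The arithmetic ratio is about 0.95 in both cases.

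Median: if every off-drug value lies below the pooled median, that median sits at the on-drug percentile (0.5 - p)/(1 - p). This is 0.45/0.95, about the 47th, for p = 5%, and 0.40/0.90, about the 44th, for p = 10%.

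Relative spread: if on- and off-drug values share a CV of c, the pooled CV² is [c²(1 - p + pr²) + p(1 - p)(1 - r)²] / (1 - p + pr)². Because 1 - p + pr² is at least (1 - p + pr)², this exceeds c² whenever r < 1 and 0 < p < 1.

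**The case against.** The strongest reply is that nothing in the documents shows this happening. ET procedures are due when the subject discontinues, no off-drug gap is planned, and no off-drug share or half-life is given. SAP 5.4 covers events as well as deviations, and SAP 10.1 reaches any circumstance that alters the PK evaluation. Having taken no dose on the sampling day can be read into its example. Naming ET as an included visit type need not override that section. The tables are descriptive, and the population PK/PD work is reported separately and can use recorded dose and sample times. The geometric mean is the statistic most sensitive to low values and is reported only where appropriate. The median, range and percentage below quantification appear alongside it and would partly expose washed-out samples.

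Most of this stands, and it limits the point. It does not remove it: the inclusion of ET samples is written as a rule, while the exclusion route is optional and silent on stopped drug, so two analysts could build different tables from the same text. For serum prolactin that route is absent.

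A reader might go further and infer any of the following, which the documents do not support:
- **Contamination is certain.** It depends on when ET visits fall after the last dose.
- **The comparison of 200 with 400 mg is biased.** SAP 18 plans no between-dose test, and differential dropout is not documented.
- **The prolactin bias favours the drug.** This needs on-drug elevation and a fall after stopping, and the documents quantify neither. The Week 6 test is rank-based, and the overall count of markedly abnormal values uses every postbaseline result.

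**Conclusion.** The gap is real and moderate. As written, SAP 6.3 Table 1 and SAP 18 pool any off-drug ET sample with samples defined as postdose, and no firm rule prevents it. For concentrations the direction follows: off-drug values lower the mean and raise the CV. With assumed off-drug shares of 5% to 10% and residual levels of 0.1 to 0.001, the geometric mean falls by 11% to 50%. The arithmetic mean falls by about 5% at the smaller share and 9% to 10% at the larger. With r near 1 the effect is nil. For prolactin, neither direction nor size can be fixed from the documents. Primary and secondary efficacy analyses are not touched. The plan should be amended because the remedy is cheap, not because a distortion has been shown.

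**What to change.** - **SAP 6.3 Table 1 and SAP 18:** include an ET amisulpride or plasma prolactin sample in the Week 2 or Week 6 by-dose summary only if it was drawn within a pre-specified time of the last recorded dose. About one dosing interval plus a visit-time allowance is suitable. A strict 24 hours would label a subject dosed at 08:00 one day and sampled at 10:00 the next as off drug.
- **Other ET samples:** list them and summarise them separately as off drug. State in SAP 10.1 that this rule governs them.
- **Serum prolactin:** keep the planned Week 6 rank ANCOVA and add a sensitivity analysis limited to on-drug samples. Removing off-drug values outright would drop subjects stopped for prolactin-type events, and that loss is itself informative.

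The data already exist. The last three dose times are on the CRF at Visit 6/ET (Protocol 11.6.3), sample times are recorded (Protocol Appendix III), and the last-dose date is derived under SAP 14. The cost is one rule, one derivation, one extra analysis and slightly fewer samples in the Week 2 and Week 6 summaries.

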18.1. DERIVATION

LLOQ is 0.0500 ng/mL for R-amisulpride and S-amisulpride and LLOQ is 1.56 ng/mL for plasma prolactin.

Below derivations apply after concentrations lower than LLOQ are set to $\frac{1}{2}$ LLOQ.

- Coefficient of variation
$$100 * \text{Standard Deviation} / \text{Mean}$$
- Geometric Mean
$$\text{Exponential}(\text{mean of } \log_e \text{ transformed data})$$
- Geometric CV
$$\text{Square Root}(\text{Exponential}(\text{Variance}(\log_e \text{ transformed data}) - 1)) * 100$$

19. DATA NOT SUMMARIZED OR PRESENTED

Disposition, demographics, and pretreatment events will be listed for screened subjects including the screen failures. A randomized subject's any premedication data from his/her screen failed period will be included in ADAM and in Tables/Lists. Any pre-treatment medical occurrences from the subject's screen failed period will be excluded from ADAE and all other screen failed period data will be excluded from any baseline calculations for the later randomized subject. The information on scales collected on paper is not included in ADAM and in Tables/Lists. Other data that are collected on screen failures will not be presented, but will be available in the clinical study database and SDTM domains.

Document:

Author:

Version Number:

V2.0

Version Date:

21MAY2020

Template No: CS_TP_BS016 Revision 4
Effective Date: 01Apr2016

Reference: CS_WI_BS005

20. CHANGES IN THE ANALYSIS SPECIFIED IN THE STATISTICAL ANALYSIS PLAN

Any changes or deviations during the analysis and reporting process from the statistical analysis plan designed will be described and justified in the final report.

Document:

Author:

Version Number:

V2.0

Version Date:

21MAY2020

Template No: CS_TP_BS016 Revision 4
Effective Date: 01Apr2016

Reference: CS_WI_BS005

APPENDIX 1. PROGRAMMING CONVENTIONS FOR OUTPUTS

OUTPUT CONVENTIONS

Where applicable, the Appendix_Compilation_Working_Guidelines_Final 07May2014.pdf document – provided by Sunovion – will be followed.

In addition, the following output conventions are to be followed:

- o The first row in the body of the table or listing should be blank
- o The left-hand column should start in column 1. No indenting or centering of the output should occur.
- o Rounding should be done with the SAS function ROUND.
- o Numbers in tables should be rounded, not truncated.
- o Alphanumeric output should be left aligned.
- o Numbers should be decimal point aligned.
- o Whole numbers should be right aligned.
- o Text values should be left aligned.
- o The first letter of a text entry should be capitalized.
- o The width of the entire output should match the linesize (134)

- **Univariate Statistics:**

If the raw data has N decimal places, then the summary statistics should have the following decimal places:

- o Minimum and maximum: N
- o Mean, median, Q1, and Q3: N + 1
- o SD: N + 2

- **Frequencies and percentages (n and %):**

- o Percent values should be reported inside parentheses, with one space between the count (n) and the left parenthesis of the percentage. Parentheses should be justified to accept a maximum of 100.0 as a value and padded with blank space if the percent is less than 100.0.
- o Percentages will be reported to one decimal place, except cases where percent <100.0% but >99.9% will be presented as '>99.9%' (eg, 99.99% is presented as >99.9%); and cases where percent < 0.1% will be presented as '<0.1%' (eg, 0.08% is presented as <0.1%). Rounding will be applied after the <0.1% and >99.9% rule.
- o Where counts are zero, no percentage should appear in the output.

- **Confidence Intervals:**

- o Confidence intervals and estimates are presented to one place more than the raw data, and standard errors to two places more than the raw data.
- o Confidence intervals should be justified so that parentheses displayed on consecutive lines of a table “line up”.
- o Boundary values of confidence intervals should be separated by a comma.

Document:

Author:

Version Number:

V2.0

Version Date:

21MAY2020

Template No: CS_TP_BS016 Revision 4
Effective Date: 01Apr2016

Reference: CS_WI_BS005

- o Boundary values should be padded as necessary to accept negative values and to allow alignment of the decimal place.
- P-values:
 - o P-values should be reported to three decimal places, except values <1.000 but >0.999 will be presented as '>0.999' (eg, 0.9998 is presented as >0.999); and values <0.001 will be presented as '<0.001' (eg, 0.0009 is presented as <0.001). Rounding will be applied after the <0.001 and >0.999 rule.
- Ratios:
 - o Ratios should be reported to one more decimal place than the raw data.
- Spacing:
 - o There must be a minimum of 1 blank space between columns (preferably 2).
- Missing values:
 - o A "0" should be used to indicate a zero frequency.
 - o A blank will be used to indicate missing data in an end-of-text table or subject listing.
- Figures:
 - o Figures should be provided in RTF files using the SAS Output Delivery System (ODS), as Computer Graphics Metafile (CGM) formatted graphical output generated by SAS.
 - o The CGM file itself should contain the title or footer.
 - o The image should be clear and of high quality when viewed in the Word document, and when printed.
 - o In general, boxes around the figures should be used.
- Footers should be defined as follows:
 - o A continuous line of underscores ('_') will follow the body of the table or listing prior to any footnotes at the bottom of the page.
 - o Table footnotes should be defined using compute statements in the proc report, and should appear directly after the body of the table.
 - o If text wraps across more than one line (for a note), the first letter for all lines of text after the first one will be indented to align beneath the first letter of the text in the first line.

DATES & TIMES

Depending on data available, dates and times will take the form DDMMYYYYYYThh:mm:ss.

Document:

Author:

Version Number:
Version Date:

V2.0

21MAY2020

Template No: CS_TP_BS016 Revision 4
Effective Date: 01Apr2016

Reference: CS_WI_BS005

SPELLING FORMAT

English US.

PRESENTATION OF TREATMENT GROUPS

For outputs, treatment groups will be represented as follows and in that order:

Treatment Group	For Tables, Graphs and Listings
Placebo	Placebo
SEP-4199 200 mg	SEP-4199 200 mg
SEP-4199 400 mg	SEP-4199 400 mg
All SEP-4199	All SEP-4199 (only applies to tables)

LISTINGS

All listings will be sorted by the following (unless otherwise indicated in the template):

- Randomized/Actual treatment received as applicable, displaying SEP-4199 first and then placebo.
- Subject ID,
- Original date/time (where applicable) - listings of AEs, concomitant medications, medical histories etc should be sorted in chronological order, with earliest AE, medication or history coming first,
- For listings where non-randomized subjects are included, these will appear in a category after the randomized treatment groups labelled 'Not Randomized'.

Document:

Author:

Version Number:

V2.0

Version Date:

21MAY2020

Template No: CS_TP_BS016 Revision 4
Effective Date: 01Apr2016

Reference: CS_WI_BS005

